### **3.3 Adjudication Committee**

An Adjudication Charter will be established and will describe the process for the surveillance, monitoring, and adjudication by the Clinical Adjudication Committee of events of post-treatment elevations of ALT and/or AST  $\geq 3 \times$  ULN. The purpose of this charter will be to provide a standardized process for the adjudication of the events in order to determine whether the elevation was related to atogepant.

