11.1 ADVERSE EVENTS

Adverse events will be coded by system organ class and preferred term using the *Medical Dictionary for Regulatory Activities* (MedDRA), version 22.0 or newer.

An AE will be considered as a treatment-emergent adverse event (TEAE) if the AE began or worsened (increased in severity or became serious) on or after the date of the first double-blinded dose of the lead-in study treatment. An AE that occurs more than 30 days after the last dose of study treatment in this study or safety follow-up visit (Visit 12) whichever comes later will not be counted as a TEAE. Per case report form instructions, a new AE record will be created for any AE that worsens; therefore, TEAEs can be identified as those AEs with recorded onset date on or after the date of the first dose of lead-in study treatment and within 30 days after the last dose of open-label study treatment or Visit 12 whichever comes later. An AE will be considered as a treatment-emergent SAE (TESAE) if it is a TEAE that also meets SAE criteria. TEAEs that started after the date of last dose of open-label study treatment will be considered as newly emergent. Only TEAEs that started on or after the date of first dose of open-label study treatment will be summarized for this study.

Overall summary of AEs will be provided on a per-participant basis for categories of TEAEs, treatment-related TEAEs, deaths, TESAEs, and TEAEs leading to study intervention discontinuation.

The number and percentage of participants reporting TEAEs will be tabulated by system organ class and preferred term, and further categorized by severity and causal relationship to the study treatment. If more than 1 AE is coded to the same preferred term for the same participants, the participant will be counted only once for that preferred term using the greatest severity and strictest causality for the summarization by severity and causal relationship.

The number and percentage of participants reporting newly emergent TEAEs will be tabulated by system organ class and preferred term.

The number and percentage of participants who have TEAEs leading to premature discontinuation of the study intervention will be summarized by system organ class, preferred term.

The incidence of common ($\geq 2\%$ [after rounding] of participants) TEAEs will be summarized by preferred term.

The number and percentage of participants who have TESAE will be tabulated by system organ class and preferred term.

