11.2 CLINICAL LABORATORY PARAMETERS

Descriptive statistics for clinical laboratory values (in SI units) at baseline, postbaseline, and changes from baseline values at each postbaseline timepoint will be presented for the following laboratory parameters.

In addition, descriptive statistics for values and changes from the baseline values in conventional units at each assessment time point will be presented for selected clinical laboratory parameters listed in [Appendix I](#). A description of reporting the lab values in conventional units in patient narratives (along with the standard reporting in SI units) is presented at the end of [Appendix I](#).

Hematology: Hemoglobin, hematocrit, red blood cell count, red blood cell indices (mean corpuscular volume, mean corpuscular hemoglobin, mean corpuscular hemoglobin concentration), white blood cell count, including differential (neutrophils, lymphocytes, monocytes, eosinophils, and basophils), platelet count

Chemistry: Sodium, potassium, chloride, bicarbonate, glucose, blood urea nitrogen, creatinine, total bilirubin, alkaline phosphatase, aspartate aminotransferase, alanine aminotransferase, lactate dehydrogenase, creatine kinase, total protein, albumin, calcium, phosphorus, uric acid, total cholesterol, estimated glomerular filtration rate

Urinalysis: Specific gravity, pH

Clinical laboratory test values will be considered potentially clinically significant (PCS) if they meet either the lower-limit or higher-limit PCS criteria listed in [Table 11-1](#). The number and percentage of participants who have PCS postbaseline clinical laboratory values will be tabulated. The percentages will be calculated relative to the number of participants with available non-PCS baseline values and at least 1 postbaseline assessment. The numerator will be the total number of participants with available non-PCS baseline values and at least 1 PCS postbaseline value during the study. A supportive tabular display of participants with PCS postbaseline values will be provided, including the participant identification (PID) number, baseline and all postbaseline (including non-PCS) values.

In addition, a tabular display showing all AEs that occurred in participants who had PCS postbaseline clinical laboratory values will be provided.

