The number and percentage of participants meeting each of the following criteria for postbaseline hepatic laboratory abnormalities listed in Table 11-2 will be summarized. The percentages will be calculated relative to the number of participants with at least 1 available postbaseline assessment. The numerator will be the total number of participants having at least 1 postbaseline value that meets the specific category during the study. A supportive listing will also be provided.

Table 11-2 Criteria for Hepatic Laboratory Abnormalities

Laboratory Parameter	Categories
ALT	$\geq 1 \times \text{ULN}$
	$\geq 1.5 \times \text{ULN}$
	$\geq 2 \times \text{ULN}$
	$\geq 3 \times \text{ULN}$
	$\geq 5 \times \text{ULN}$
	$\geq 10 \times \text{ULN}$
	$\geq 20 \times \text{ULN}$
AST	$\geq 1 \times \text{ULN}$
	$\geq 1.5 \times \text{ULN}$
	$\geq 2 \times \text{ULN}$
	$\geq 3 \times \text{ULN}$
	$\geq 5 \times \text{ULN}$
	$\geq 10 \times \text{ULN}$
	$\geq 20 \times \text{ULN}$
ALT or AST	$\geq 1 \times \text{ULN}$
	$\geq 1.5 \times \text{ULN}$
	$\geq 2 \times \text{ULN}$
	$\geq 3 \times \text{ULN}$
	$\geq 5 \times \text{ULN}$
	$\geq 10 \times \text{ULN}$
	$\geq 20 \times \text{ULN}$
Bilirubin Total	$\geq 1 \times \text{ULN}$
	$\geq 1.5 \times \text{ULN}$
	$\geq 2 \times \text{ULN}$
	$\geq 3 \times \text{ULN}$
	$\geq 5 \times \text{ULN}$
	$\geq 10 \times \text{ULN}$
	$\geq 20 \times \text{ULN}$
Alkaline Phosphatase	$\geq 1 \times \text{ULN}$
	$\geq 1.5 \times \text{ULN}$
	$\geq 2 \times \text{ULN}$
	$\geq 3 \times \text{ULN}$
	$\geq 5 \times \text{ULN}$
	$\geq 10 \times \text{ULN}$
	$\geq 20 \times \text{ULN}$

Laboratory Parameter	Categories
Concurrent Elevations ¹	ALT or AST $\geq 3 \times$ ULN and Bilirubin Total $\geq 1.5 \times$ ULN ALT or AST $\geq 3 \times$ ULN and Bilirubin Total $\geq 2 \times$ ULN
Potential Hy's Law within 24-hour window ¹	Postbaseline assessment of the following laboratory parameters based on blood draws collected within a 24-hour period: 
• ALT or AST $\geq 3 \times$ ULN• TBL $\geq 2 \times$ ULN• ALP $< 2 \times$ ULN
e-DISH	Postbaseline assessment of the following laboratory parameters at any time: 
• Maximum ALT or AST $\geq 3 \times$ ULN• Maximum TBL $\geq 2 \times$ ULN

ALT = alanine aminotransferase; AST = aspartate aminotransferase; TBL = total bilirubin;
ALP = alkaline phosphatase; ULN = upper limit of normal (value provided by the laboratory).

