¹ Elevations are from the same day

The number and percentage of participants with an adjudicated case (i.e., ALT $\geq 3 \times$ ULN and/or AST $\geq 3 \times$ ULN) will be summarized and by relationship of ALT or AST elevation to study medication. The percentages will be calculated relative to the number of participants with at least 1 adjudicated case. The numerator will be the number of participants with at least 1 adjudicated case in the specific category of relationship. If a participant has more than 1 adjudicated case, he or she will be counted in the most relevant category of relationship.

Participants with an adjudicated case (i.e. ALT $\geq 3 \times$ ULN or AST $\geq 3 \times$ ULN) will be listed with their ALT and AST assessments, adjudication dates, relationship of ALT or AST elevation to study medication, and confounding factor(s). Additional listings will be provided for participants who meet ALT $\geq 3 \times$ ULN or AST $\geq 3 \times$ ULN and/or potential Hy's law and have one of the following categories: at least 1 abnormal liver biochemistry risk factor, at least 1 liver disease sign and symptom, at least 1 liver diagnostic test performed, consultation with a specialist for liver evaluation, liver lab tests performed, and drug screen performed, respectively.

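### SAP 11.2 expresses adjudicated ALT/AST cases only as a percentage of participants with a case, and the same-day footnote to Table 11-2 contradicts the 24-hour Hy's law window

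*SAP*

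**What the plan says.** **Adjudicated cases.** After Table 11-2, SAP 11.2 promises "The number and percentage of participants with an adjudicated case", in total and by the relationship of the elevation to study medication. One denominator is given: "The percentages will be calculated relative to the number of participants with at least 1 adjudicated case". The numerator rule is "The numerator will be the number of participants with at least 1 adjudicated case in the specific category of relationship". The SAP also plans a listing of every adjudicated case with its ALT and AST values, relationship and confounding factors.

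**Neighbouring tables.** For the hepatic abnormalities in Table 11-2, which include a row for ALT or AST at or above 3 x ULN, the rule is "The percentages will be calculated relative to the number of participants with at least 1 available postbaseline assessment". For potentially clinically significant (PCS) laboratory values it is "The percentages will be calculated relative to the number of participants with available non-PCS baseline values and at least 1 postbaseline assessment".

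**Purpose of adjudication.** Protocol 3.3 sets up the committee process "in order to determine whether the elevation was related to atogepant". Adverse events in SAP 11.1 are "further categorized by severity and causal relationship to the study treatment", but that causality is the investigator's assessment (Protocol 9.1.4), not the committee's.

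**Hy's law window.** Footnote 1 to Table 11-2 reads "Elevations are from the same day". Its marker stands on two rows: concurrent elevations, and potential Hy's law. The second row's own label and text, the definition in the body of SAP 11.2, and Protocol 9.5.1 all refer to 24 hours. Protocol 9.5.1 expressly allows the analytes to come from more than one sample in that time.

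**The concern.** The committee exists to separate related from unrelated elevations, and ALT or AST at or above 3 x ULN is an adverse event of special interest (Protocol 6.5.2). The natural summary is how many of the participants assessed had an elevation judged related. No planned percentage gives this. Table 11-2 has the right denominator but no relationship. The adverse event tables have a relationship, but not the adjudicated one. The adjudication table has the adjudicated relationship, but divides by cases. Its percentage therefore moves with the number of unrelated cases even when the related risk is unchanged.

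The footnote is a different kind of problem, because it puts two rules on one row. A programmer who applied the same-day rule could leave a qualifying participant out of the potential Hy's law count. That too is a named event of special interest.

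**Working it through.** The documents state no figure on this point, so there is nothing to reproduce. The check applies the written rules literally.

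**Inputs.** Planned enrolment is about 750 (SAP 16.0), used here as the number assessed; 700 is an assumed lower value. Case counts are not in the documents. I assume 4 to 15 adjudicated cases, of which 1 or 2 are judged related.

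**1. Overall line.** With k participants who have a case, the stated denominator gives k/k = 100% for any k above zero, and 0/0 if there is none. With the Table 11-2 denominator, 8 cases would give 8/750 = 1.07%. The range is 4/750 = 0.53% to 15/700 = 2.14%.

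**2. Relationship rows.** The planned percentage is related cases divided by all cases. The percentage not planned is related cases divided by participants assessed.

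| Related | Cases | Planned (share of cases) | Per 750 assessed |
|---|---|---|---|
| 2 | 4 | 50% | 0.27% |
| 2 | 8 | 25% | 0.27% |
| 2 | 15 | 13.3% | 0.27% |
| 1 | 15 | 6.7% | 0.13% |

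The first three rows have the same related risk and three different printed percentages. The reverse also happens: 3 of 10 and 30 of 100 both print as 30%, but per 750 assessed they are 0.4% and 4.0%. Over the assumed ranges the share runs from 1/15 = 6.7% to 2/4 = 50%, and the percentage of those assessed from 1/750 = 0.13% to 2/700 = 0.29%. These are two different quantities, so the distance between them is not the size of an error.

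**3. Same day against 24 hours.** Two draws on one calendar date are always less than 24 hours apart, so every same-day pair meets the 24-hour rule. The converse fails: draws at 16:00 and at 10:00 the next morning are 18 hours apart, so they meet the 24-hour rule and fail the same-day rule. The footnote is strictly narrower and can only remove cases. One such participant moves the potential Hy's law row between 0/750 = 0% and 1/750 = 0.13%.

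**4. Would the participant disappear?** No. The e-DISH row of Table 11-2 uses maximum values at any time and would still include the participant. For the concurrent elevations row no 24-hour rule is stated, so the footnote contradicts nothing there.

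**The case against.** A share of adjudicated cases is a legitimate descriptive statistic, and the SAP states its denominator openly. Incidence regardless of relationship is already in Table 11-2, the related count is printed beside its percentage, and every case is listed. A reader can do the division. All of this stands, and it limits the point to one percentage that should be printed and is not.

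The 100% overall figure is the literal reading. The numerator sentence covers only the relationship categories, and the table specifications are in a separate document that I have not seen (SAP 4.0), so the overall line may be laid out differently. That also stands, but the SAP text should not depend on it.

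The denominators within SAP 11.2 are not uniform either: the PCS tables also require a non-PCS baseline. True, but both the PCS and the Table 11-2 rules count participants assessed, and the adjudication rule does not.

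On the footnote, three statements in the SAP (body text, row label and row text) give 24 hours, Protocol 9.5.1 agrees, and the protocol expects the analytes typically to come from one sample. A careful programmer would probably follow the majority. This makes loss of a case unlikely, but the contradiction remains.

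A reader might infer three stronger things that the documents do not support:

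- That the SAP hides the risk of related liver elevations. The counts and listings are planned, so it does not.
- That a corrected overall row must equal the Table 11-2 row for ALT or AST at or above 3 x ULN. Adjudication covers post-treatment elevations under a charter not seen here, while Table 11-2 counts postbaseline values against a lead-in baseline. The two may legitimately differ.
- That Hy's law cases could go unreported. Site reporting follows Protocol 9.5.1 and is untouched by a table footnote.

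**Conclusion.** The point holds as a small correction to two descriptive safety tables. As written, adjudicated ALT/AST cases are given only as a percentage of participants with a case. On a literal reading the overall percentage carries no information, and the adjudicated-related risk per participant assessed has to be worked out by the reader. That conclusion follows from the stated denominator and does not depend on the assumed case counts; only the illustrative percentages do.

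The same-day footnote is a plain inconsistency with the 24-hour definition. Its likely effect is nil or one participant, about 0.13% of 750, and only if the qualifying draws fall on two calendar dates.

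The study is single-arm and descriptive, and no test, sample size or clinical rule depends on either item.

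**What to change.** 1. In SAP 11.2, for adjudicated cases overall and by relationship, take as denominator the participants with at least one postbaseline ALT/AST assessment, as in Table 11-2. Keep the share among cases as a second column, labelled as such. Add a note that the overall row need not equal the Table 11-2 row for ALT or AST at or above 3 x ULN.
2. In Table 11-2, remove the footnote 1 marker from the potential Hy's law row, so that the row follows the 24-hour window in the SAP text and in Protocol 9.5.1. Leave the footnote on the concurrent elevations row.

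The cost is a changed sentence, one extra column, a short note and one footnote marker. All the data are already planned for collection. The only drawback is a slightly wider table.

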11.3 VITAL SIGNS

Descriptive statistics for vital signs (systolic and diastolic blood pressures [sitting and standing], pulse rate [sitting and standing], respiratory rate, temperature, weight, orthostatic systolic blood pressure, orthostatic diastolic blood pressure, and orthostatic pulse rate) values at baseline, postbaseline, and changes from baseline values at each postbaseline timepoint will be presented. Orthostatic vital sign values (orthostatic systolic and diastolic blood pressures, and orthostatic pulse rate) are defined as the corresponding standing measurement minus sitting measurement of systolic and diastolic blood pressures and pulse rate respectively.

Vital sign values will be considered PCS if they meet both the observed value criterion and the change from baseline value criterion, if both criteria are available, or meet either the observed value criterion or the change from baseline value criterion that will be detailed in [Table 11-3](#). The number and percentage of participants who have PCS postbaseline vital sign values will be tabulated. For criteria related with systolic blood pressure, diastolic blood pressure, pulse rate and weight, the denominator will be the number of participants who have available baseline and at least 1 postbaseline assessment. For criteria related with orthostatic measures, the denominator will be the number of participants who have available non-PCS baseline and at least 1 postbaseline assessment. The numerator will be the total number of participants with at least 1 PCS postbaseline value during the study. A supportive listing of participants with PCS postbaseline values will be provided. In addition, a tabular display showing all AEs that occurred in participants who had PCS postbaseline vital sign values will be provided.

Table 11-3 Criteria for Potentially Clinically Significant Vital Signs

Parameter	Flag	Criteria	
		Observed Value	Change from Baseline
Systolic blood pressure, mm Hg	High	≥ 180	Increase of ≥ 20
	Low	≤ 90	Decrease of ≥ 20
Diastolic blood pressure, mm Hg	High	≥ 105	Increase of ≥ 15
	Low	≤ 50	Decrease of ≥ 15
Pulse rate, bpm	High	≥ 120	Increase of ≥ 15
	Low	≤ 50	Decrease of ≥ 15
Weight, kg	High	—	Increase of $\geq 7\%$
	Low	—	Decrease of $\geq 7\%$
Orthostatic SBP change, mm Hg	Low	≤ -20	—
Orthostatic DBP change, mm Hg	Low	≤ -15	—
Orthostatic Pulse rate change, bpm	High	≥ 25	—

SBP = Systolic blood pressure, DBP = Diastolic blood pressure, bpm = beats per minute.

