11.4 ELECTROCARDIOGRAM

Descriptive statistics for ECG parameters (ie, heart rate, PR interval, QRS interval, QT interval, and QTc interval) at baseline, postbaseline, and changes from baseline values at each postbaseline timepoint will be presented.

ECG parameter values are considered PCS if ECG values meet either the actual value or change from baseline PCS high criteria listed in [Table 11-4](#). The number and percentage of participants with PCS postbaseline values will be tabulated. The percentages will be calculated relative to the number of participants with an available non-PCS baseline value and at least 1 postbaseline assessment. The numerator will be the total number of participants with an available non-PCS baseline value and at least 1 PCS postbaseline ECG value during the study. A supportive listing of participants with PCS postbaseline values will be provided. A listing of all AEs for participants with PCS ECG values will also be provided.

To evaluate ECG postbaseline values of clinical interest, the number and percentage of participants with post-treatment QTcF >450 ms, >480 ms, or >500 ms will be tabulated by treatment group. A supportive listing of participants with postbaseline clinical interest will be provided. A listing of all AEs for participants with postbaseline clinical interest will also be provided.

The number and percentage of participants with an increase > 30 msec but ≤ 60 msec, and with an increase > 60 msec in QTcF will be tabulated. Participants will be counted only once for the most severe category. A supportive listing of participants with postbaseline QTcF increases > 30 msec will be provided, including the PID number, study center, and all QTc values (including changes from baseline). A listing of all AEs for participants with postbaseline QTcF increases > 30 msec will also be provided.

A shift table from baseline to the end of open-label treatment period in the investigator's overall interpretation of the ECG will be presented for the following categories: normal; abnormal, not clinically significant; abnormal, clinically significant. A tabular display of participants with postbaseline clinically significant ECG abnormalities according to the investigator's overall interpretation will be provided.

Table 11-4 Criteria for Potentially Clinically Significant Electrocardiograms

Parameter	Unit	Criterion
QRS interval	msec	≥ 150
PR interval	msec	≥ 250
QTc (QTcB or QTcF) interval	msec	> 500

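### For the three orthostatic criteria in SAP 11.3, the numerator lacks the non-PCS-baseline condition that the denominator imposes

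*SAP*

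**What the plan says.** SAP 11.3 sets two denominators for the PCS vital-sign percentages.

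- Systolic pressure, diastolic pressure, pulse rate and weight: "the denominator will be the number of participants who have available baseline and at least 1 postbaseline assessment".
- Orthostatic measures: "the denominator will be the number of participants who have available non-PCS baseline and at least 1 postbaseline assessment".

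One numerator sentence follows and serves both groups: "The numerator will be the total number of participants with at least 1 PCS postbaseline value during the study". It sets no condition on baseline.

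A value is PCS when "they meet both the observed value criterion and the change from baseline value criterion, if both criteria are available"; where Table 11-3 lists only one type of criterion, that one suffices. The three orthostatic rows list an observed-value criterion only: standing minus sitting systolic pressure of -20 mm Hg or lower, diastolic pressure of -15 mm Hg or lower, and pulse of 25 bpm or higher.

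The laboratory and ECG sections also use a non-PCS-baseline denominator, and both repeat the condition in the numerator. SAP 11.2: "The numerator will be the total number of participants with available non-PCS baseline values and at least 1 PCS postbaseline value during the study". SAP 11.4: "The numerator will be the total number of participants with an available non-PCS baseline value and at least 1 PCS postbaseline ECG value".

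**The concern.** A denominator limited to participants who were not PCS at baseline is there to give the rate of new findings. That works only if the numerator is drawn from the same people. In the orthostatic rows it is not, so a finding that was present before treatment can be counted as one that arose on study.

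Baseline here is the last assessment before the first lead-in dose (SAP 11.0 and 18.3), so the participants wrongly added either had the finding before any study drug or had no baseline to compare with. Safety and tolerability are this study's only objective, and interim data-cuts are meant to support regulatory submissions. The orthostatic percentages should therefore mean what a reader will take them to mean.

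**Working it through.** The plan states no figure for these rows, so there is none to reproduce. The check compares the rules and then works out what the mismatch does.

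**Step 1. Which rows are affected.** In Table 11-3 the systolic, diastolic and pulse-rate criteria need both an observed value and a change from baseline, and the weight criterion is a percentage change from baseline. I read availability of a criterion as a property of the table row. A participant who is PCS on any of these must then have a baseline and a postbaseline value, and so is in that denominator. The shared numerator sentence does no harm there. The orthostatic rows have no change criterion. The orthostatic value is a standing-minus-sitting difference at a single assessment, so it can be PCS at baseline, and it can be PCS later when baseline is missing. The mismatch is confined to these three rows.

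**Step 2. Whether another section supplies the condition.** SAP 18.3 says that all postbaseline assessments feed the PCS determination and adds no baseline restriction. I found none elsewhere in the SAP. SAP 4.0 places table specifications in a separate document, which is not available here.

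**Step 3. Whether such participants can exist.** The blood-pressure exclusion in Protocol 4.3 is on sitting pressure; no listed criterion sets an orthostatic limit. Sitting and standing readings are scheduled at every in-person visit, and one PCS value is enough. A participant who was PCS at baseline has up to 10 in-person treatment visits (Visits 2 to 11), plus any in-person Visit 12, at which to qualify.

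**Step 4. The arithmetic.** Let D be the orthostatic denominator, x the participants in D who are PCS postbaseline, and y the PCS participants outside D.

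- Matched percentage = x/D
- Percentage as written = (x + y)/D
- Excess = y/D, which is zero or positive

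For participants who were PCS at baseline, let b be their share of N and r the share of them who are PCS again. With complete baseline and postbaseline data, D = N(1 - b) and y = N·b·r, so the excess is b·r/(1 - b). The incidence among the others does not enter. Participants with a missing baseline are not in this formula and would add to y.

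**Step 5. Illustration.** Only N = 750 (SAP 16.0) comes from the documents. The values of b and r and the matched rate of 10% are assumptions.

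| b | D | r | y | Excess (points) | As written, if matched = 10.0% |
|---|---|---|---|---|---|
| 0% | 750 | any | 0 | 0 | 10.0% |
| 1% | 742.5 | 30% | 2.25 | 2.25/742.5 = 0.30 | 10.3% |
| 1% | 742.5 | 60% | 4.50 | 4.50/742.5 = 0.61 | 10.6% |
| 5% | 712.5 | 30% | 11.25 | 11.25/712.5 = 1.58 | 11.6% |
| 5% | 712.5 | 60% | 22.50 | 22.50/712.5 = 3.16 | 13.2% |

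One mismatched participant adds 100/750 = 0.133 to 100/712.5 = 0.140 points. The relative effect is larger when the true rate is low: at b = 5% and r = 30%, a matched 2.00% becomes 3.58%, while a matched 10.00% becomes 11.58%.

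**Step 6. Limiting case.** Because the numerator is not contained in the denominator, the result is not bounded by 100%. With b = 10% and every participant PCS postbaseline, it is 750/675 = 111%. This shows only that the rule is not a proper proportion; it is not a realistic outcome.

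**The case against.** The strongest reply is that this is shorthand. A percentage of participants is normally read with its numerator inside its denominator, and the orthostatic denominator already shows the intent to leave out participants who were PCS at baseline. A programmer may apply the restriction without being told, and the table specifications may state it. That is possible, so an inflated percentage in the final tables is not established. But SAP 11.2 and 11.4 do spell the condition out, so a reader comparing the sections could take its absence from 11.3 as deliberate, and two programmers could produce different tables from the same text.

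The second reply is that the worked percentages rest on assumed inputs and that other choices move them a long way. This stands. With b = 10% and r = 80% the excess would be 60/675 = 8.9 points; with b or r at zero, and no participant with a missing baseline who is PCS later, it is nil. The illustration shows how the error behaves and does not predict its size.

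The third is that little turns on it: three descriptive rows in a single-arm study with no formal test, an error that can only overstate a finding, and listings that would let a careful reader see who was PCS at baseline. All of this is true and limits the importance of the point. It does not make the stated rule correct.

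**Conclusion.** The concern holds. For the three orthostatic criteria, SAP 11.3 as worded produces a percentage whose numerator can include people its denominator excludes. The error runs one way: the reported percentage is at least the matched one, and exceeds it whenever a participant who was PCS or missing at baseline is PCS afterwards.

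The size cannot be fixed from the documents. Under the assumptions b = 0 to 5%, r = 0 to 60% and complete data, the excess is 0 to 3.2 percentage points. Blood pressure, pulse rate and weight are unaffected, and no test, sample size or decision rule depends on these rows. The wording gap is certain; whether it reaches the tables depends on specifications not seen here.

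**What to change.** Keep the present numerator sentence for systolic pressure, diastolic pressure, pulse rate and weight. Add one sentence for the orthostatic criteria: only participants who have an orthostatic baseline that is not PCS, and who then have one or more PCS values after baseline, are counted in the numerator. This is the form already used in SAP 11.2 and 11.4. Check that the separate table specifications say the same.

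Participants who were already PCS at baseline, or had no baseline, should stay in the supportive listing, so no safety information is lost. The cost is one SAP sentence and one programming filter on data already collected.
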